## 2. BACKGROUND

ASD is a heterogeneous neurodevelopmental disorder often with life-long consequences that affects young children during critical times in their development. The latest estimates from the Center for Disease Control estimates an ASD affects as many as 17 per 1000 children (1 in 59) in the United States with recently estimation demonstrating that the prevalence continues to rise. ASD is defined by impairments in social communication as well as the presence of restrictive interests and repetitive behaviors. ASD is frequently associated with co-occurring problems such as gastrointestinal abnormalities, seizures, attention deficits, anxiety and allergies - to name a few.

Full Study Title: Effect of a Wide Spectrum Nutritional Supplement on Mitochondrial Function in Children with Autism Spectrum Disorder (ASD)

Principal Investigator: [name]; Co-Investigators: [name]

Sponsor: [name]; IND 142751; ClinicalTrials.gov ID: NCT03835117; Protocol Version 02/11/2022

Funding Source: Turnabout for Autism (Private Foundation), Pleasanton CA.

Despite the fact that the prevalence of ASD has dramatically increased over the past two decades, there currently is no effective medical treatment for children with ASD. A recent multicenter study showed that optimal outcomes can be achieved in a subset of ASD children. Moreover, a study that analyzed the annual change in ASD symptoms in 6,975 children showed that some children with ASD can substantially improve. However, these studies did not address whether particular therapies were associated with better outcomes. In addition, the findings suggest that only a minority of children with ASD show substantial improvement over time, underscoring the need for more effective treatments.

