### Clinical Abnormalities Found in Mitochondrial Disease

Not Typically Clinically Abnormal in ASD	Clinically Abnormal in Some ASD Individuals
Ophthalmoplegia	Stroke-like episodes
Facies myopathica	Migraine
Hematology, Vision	Cortical blindness
Hearing, Brainstem abnormalities	Development Delay
	Loss of Skills
	Seizures
	Muscle Weakness
	Peripheral Neuropathy
	Abnormalities in Endocrine/Growth, Gastrointestinal System, Lactate, Pyruvate, Alanine

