## **Medical Assessments**

9. **Medical and Psych History**: This structured questionnaire form assists with the elicitation and assessment of health complaints, appetite, sleep, activity level and general health at **baseline**. The companion measure, the Adverse Effects Review, is used in follow up visits to monitor and document new events during the trial.

10. **Suicidality Assessment**: Although we do not anticipate any symptoms consistent with suicidality, an assessment of suicidality is required in FDA trials involving psychiatric disorders including ASD and is a standard assessment in FDA regulated ASD trials. An assessment similar to other studies examining ASD children will be used. The Columbia-Suicide Severity Rating Scale (C-SSRS) fulfills this requirement.

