## **Statistical Analysis**

All data analysis for the primary study aims will be conducted by the principal investigator. The primary analysis will be intent-to-treat, defined as all randomized subjects. Exploratory “per protocol” analysis will be conducted on participants who adhered to protocol. Analyses will be performed with R 3.02 (<http://www.r-project.org>) or SAS 9.3 (SAS Institute, Cary, NC).

Sample Size Justification and Power Analysis: Assuming a medium effect size of 0.5, the study provides an 80% power assuming a 0.01 alpha (allowing correction for multiple primary end-points)..

Primary Hypothesis: After 12 weeks of taking the nutritional supplement will improve mitochondrial function more than taking the placebo for 12 weeks. To test this hypothesis, we will use a mixed model using baseline and all post-randomization measures of mitochondrial activity. To deal with missing post-treatment data, the model will be conditioned on all baseline values. This conditional joint response model is more tolerant of missing data than ANCOVA and is less biased than carrying baseline data forward to endpoint.

Safety analyses: Adverse events (AE) will be systematically monitored using a 34-item form. It includes specific queries about major body systems, activity level, sleep, appetite, and general health. New events, whether presumed related to treatment or not, are classified as AEs and rated as Mild, Moderate or Severe (see details below). The occurrence of an AE will be counted once at the highest level of severity (e.g., a report of mild nausea followed by a report of moderate nausea in the same child would count as an occurrence of moderate nausea). The frequency of AEs by severity will be evaluated using a Fisher’s exact test. We will pursue exploratory analyses such as survival analyses using time to AE as the response variable.

Validation of the CGI-ASD: In addition to the standard CGI-S and CGI-I we will use a new a structured CGI rating scale called the CGI-S-ASD and CGI-I-ASD respectively. We will compare the performance of the standard and new CGI rating scales. Since the CGI-ASD provide guidance for completing the ratings we will have the rater complete the standard scale before the new scale. The correspondence between each scale and other outcome measures will be studied as well as the performance of the scales as outcome measures.

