## **Potential Risks**

The risks associated with these procedures include exposure to the study supplement or placebo, and the risk associated with venipuncture. The blood draws poses a possible risk of bruising at the site of the draw, light-headedness and fainting along with a remote chance of infection.

Although highly unlikely, there are potential privacy risks associated with participating in such a study. There is minimal risk associated with the completion of rating scales and assessment measures. Blood draws are common procedures and will be performed by a certified phlebotomist. We will offer a numbing cream prior to the blood drawing procedure. We will systematically review adverse at follow up phone calls and clinic visits (see below). Parents will be given phone numbers of the principal investigator and study physician – who will be available after hours. The PI and study physician have access to the pharmacy after hours – if it is necessary to break the blind.

The nutritional supplement and supplements similar to it have been on the market and used widely in the autism community. There have been few reported side effects of this supplement. They include nausea and hyperactivity, both of which resolve on their own. One similar supplement produced by [name] at Arizona State University has been studied in three clinical trials without reported significant adverse effects. In addition, the majority of the ingredients in the nutritional supplement are well within the proposed upper tolerable limits recommended by the institute of medicine and the two vitamins that exceed these limits are known to be well tolerated at doses well above the recommend upper limits. Increased consumption of B vitamins may also temporarily change urine color.

Confidentiality will be maintained throughout the project period. With the exception of tests that require date of birth, research records will not include names or contact information. Subjects will be identified only by their code numbers. A file with personal health information (e.g., names and addresses) will be kept separately in a locked file cabinet.

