### **Monitoring for Adverse Events (AEs):**

At each visit, including baseline and interim contacts, the treating clinician will systematically review for AEs and concomitant medications using an AE Review form developed for this study. We have used versions of this form, in several multi-site clinical trials in children with ASD which contains a general inquiry including several questions about daily activities (e.g., sleep, appetite, energy level, bowel and bladder functions). The general inquiry includes an open-ended question about any problems or complaints, as well as questions regarding the need for other medications and doctor or health care encounters since the last study visit. The last section includes specific questions about daily activities. All **new** AEs will be documented on the AE log. The status of previously-reported AEs

Full Study Title: Effect of a Wide Spectrum Nutritional Supplement on Mitochondrial Function in Children with Autism Spectrum Disorder (ASD)

Principal Investigator: [name]; Co-Investigators: [name]

Sponsor: [name]; IND 142751; ClinicalTrials.gov ID: NCT03835117; Protocol Version 02/11/2022

Funding Source: Turnabout for Autism (Private Foundation), Pleasanton CA.

will be monitored as well.

When the treating clinician elicits an AE, it will be documented regardless of suspected relationship to the supplement. The AE log requires the treating clinician to label the AE and to document the severity, onset, course, outcome, and attribution (study drug related or not).

Attribution is classified as follows:

- Definite: AE is clearly related to the study drug.
- Probable: AE is likely to be related to the study drug.
- Possible: AE may be related to the study drug.
- Unlikely: AE is doubtfully related to the study drug.
- Unrelated: AE is clearly not related to the study drug.

*Severity of AEs is classified as follows:*

- mild = present, but no intervention required;
- moderate = present, may be bothersome or may require intervention;
- severe = present, bothersome, requires intervention and may produce sequelae.

Decisions on the appropriate care of the subject will be made by the treating clinician (who will remain blind to treatment assignment), in collaboration with the family's primary care provider whenever possible. Abnormal findings on laboratory tests that exceed established alarm values will be investigated to determine the nature of the adverse events.

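### AEs are defined as new events only, so worsening of a symptom present at baseline, such as hyperactivity or nausea, has no stated route into the AE count

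*Combined protocol and SAP*

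**What the plan says.** Three places in the combined protocol and SAP govern what is recorded as an AE.

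- Section 6, Statistical Analysis, Safety analyses: "New events, whether presumed related to treatment or not, are classified as AEs and rated as Mild, Moderate or Severe". Each AE is then counted once, at its worst grade, and frequencies by severity go to Fisher's exact test.
- Section 5, Medical Assessments, item 9: the structured history "assists with the elicitation and assessment of health complaints, appetite, sleep, activity level and general health at" baseline. Its companion form, the Adverse Effects Review, "is used in follow up visits to monitor and document new events during the trial".
- Section 7, Monitoring for Adverse Events: "At each visit, including baseline and interim contacts, the treating clinician will systematically review for AEs". All new "AEs will be documented on the AE log. The status of previously-reported AEs" is to be followed too.

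On the side effects reported for the supplement, section 7 (Potential Risks) says: "They include nausea and hyperactivity, both of which resolve on their own". The Data Safety and Monitoring Plan has the medical monitor review adverse effects every three months.

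**The concern.** Hyperactivity is both a named side effect and something the trial expects to find at entry. The OACIS rates hyperactivity/inattention at baseline, and the ABC, whose Hyperactivity subscale is a secondary outcome, is first taken at screening. For a child who already has the symptom, harm from the product would appear as worsening and not as onset. A definition that turns on novelty is least sensitive in exactly those children.

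The AE table is what the treatments are compared on, and the medical monitor's periodic review draws on the same reports. If worsening is left out, or is left to each clinician's discretion, the safety comparison understates the harms that the protocol names.

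**Working it through.** The plan gives no figure to reproduce, because the point concerns a definition. The check takes each provision that might bring a worsening baseline symptom into the AE count.

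1. **Definition (Safety analyses).** It names new events. Worsening is neither included nor excluded.
2. **Forms (Medical Assessments, item 9).** Existing complaints go on the history form and new events on the review form. No rule connects the two when an existing complaint changes grade.
3. **Log (Monitoring for Adverse Events).** New AEs are entered and previously reported AEs are followed. A complaint held only in the history is not a previously reported AE.
4. **Counting rule (Safety analyses).** Taking the worst grade handles escalation, as in the plan's example of mild and then moderate nausea, but only once the event has been classed as an AE.
5. **Attribution rule (Monitoring for Adverse Events).** Recording an AE whatever its suspected cause settles attribution. It does not settle what counts as an event.
6. **Elicitation.** The 34-item form asks about body systems, activity level and appetite, and Table 1 schedules the AE review at baseline and weeks 1, 2, 4, 8, 12, 16, 20 and 24. Worsening may well be heard. No rule says how to class it.
7. **Other scales (Table 1).** The PRASC is taken at weeks 4, 8, 12, 16, 20 and 24, the OACIS at baseline and weeks 12 and 24, and the ABC at screening and weeks 12 and 24. None enters the AE count. Because the named side effects are said to resolve unaided, a transient worsening may be over before week 12 or 24.
8. **Serious AEs.** The definition covers any event that meets its criteria and is not limited to new ones.

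**Tracing one child.** Suppose mild hyperactivity is noted in the history and becomes severe at week 4. Under the wording as it stands, nothing is new and the AE count for that item is 0. With a worsening clause the count is 1, at grade severe. The same holds in a placebo period.

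**Illustration of direction only; every rate here is an assumption.** Take one symptom. Let its true onset-or-worsening rate be 25% on supplement and 5% on placebo, the same whether or not the child had it at baseline. Use 50 exposures per treatment, treated as independent (a simplification, since each child contributes to both). Let b be the share of children with the symptom at baseline, and suppose all their events go uncounted.

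Expected counted events = 50 × rate × (1 − b). Power is exact, for Fisher's test at two-sided 0.05.

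| b | Supplement | Placebo | Difference | Power |
|---|---|---|---|---|
| 0% | 50 × 0.25 × 1.0 = 12.5 | 50 × 0.05 × 1.0 = 2.5 | 10 | about 75% |
| 20% | 50 × 0.25 × 0.8 = 10 | 50 × 0.05 × 0.8 = 2 | 8 | about 59% |
| 40% | 50 × 0.25 × 0.6 = 7.5 | 50 × 0.05 × 0.6 = 1.5 | 6 | about 40% |
| 60% | 50 × 0.25 × 0.4 = 5 | 50 × 0.05 × 0.4 = 1 | 4 | about 19% |

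Both counts fall and the difference shrinks. Under these assumptions the ratio stays at 5 in every row (for example 12.5/2.5 and 5/1). What is lost is absolute frequency and the chance of seeing a signal.

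**The case against.** The strongest reply is that silence is not exclusion. No section says that worsening is not an AE. The log rule can be read as a guard against entering the same event twice. The review form has an open question about problems or complaints, and a clinician could enter a marked worsening as a new event. The AE review also starts at baseline, so a complaint might be entered there and then followed. All of this stands, and it means the documents do not show that worsening *will* go unrecorded. It does not supply a rule: whether the event is counted would depend on the clinician.

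It is also fair that worsening would not be invisible, given the PRASC, OACIS and ABC, and that serious worsening is covered. Those scales are outcomes, however, and do not feed the AE table.

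Three stronger readings are tempting, and the documents do not support them.

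- A reader might infer that gastrointestinal symptoms in general are named side effects. Only nausea and hyperactivity are named. New nausea in a child with some other gastrointestinal problem is still a new event.
- A reader might infer that the trial selects children who already have the side-effect symptoms. The Background says "ASD is frequently associated with co-occurring problems such as gastrointestinal abnormalities" and lists attention deficits, but not hyperactivity. The table of clinical abnormalities has one entry reading "Abnormalities in Endocrine/Growth, Gastrointestinal System, Lactate, Pyruvate, Alanine", among several found in some individuals with ASD. It names neither nausea nor hyperactivity.
- A reader might pool the two symptoms to say how many of the 50 children could never register an AE. No prevalence is given, and a child with one symptom at baseline can still register the other.

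**Conclusion.** The point holds as a gap in the AE definition. The three governing passages speak of new events, and no passage provides for worsening of a symptom present at baseline. Applied literally, the rule can make non-serious AE frequencies too low in both treatment periods and can shrink the difference between treatments, for hyperactivity and nausea in particular.

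The size is unknown. It depends on how many children have the symptom at baseline, how often it worsens on each treatment, and how often clinicians would log worsening anyway. The documents give none of these, and the table above shows direction only. The primary mitochondrial analysis and the serious AE reports are not affected. The change should be made because the gap touches the side effects the protocol itself names and the baseline information needed to close it is already collected.

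**What to change.** In Medical Assessments item 9, Safety analyses, and Monitoring for Adverse Events, use one definition: an AE is any new event, or any increase in the severity or frequency of a condition present at the reference visit, whether or not it is thought to be related to treatment.

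Add a reference grade for each item to the existing AE form. For Phase 1, take it from the history (which Table 1 places at screening) and the baseline AE review.

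For Phase 2, state whether baseline or the week-12 AE review is the reference. Week 12 ends Phase 1 and precedes the switch, so the choice decides how a symptom that arose in Phase 1 and persists is counted. Judged against baseline, it is still new or worse in Phase 2; judged against week 12, it counts only if it worsens again. Settle this before any unblinded AE table is produced.

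The cost is one extra field on the form and a somewhat higher reported AE count. No new visit or instrument is needed.

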The *primary aims* of this study are to evaluate the effect of a wide-spectrum nutritional supplement on mitochondrial function in individuals with ASD. Participants entered into the trial will have abnormalities in mitochondrial function that are associated with ASD (such abnormalities are found in approximately 50% of children with ASD) but are not diagnostic of mitochondrial disease. Specifically, children with mitochondrial disease (approximately 5% of the ASD population), which is a very severe disorder, will be excluded from the study so they can pursue more intensive appropriate treatment. As we believe 50% of children with ASD have some form of atypical variations in mitochondrial function, we will target these children to improve the function of their mitochondria. We hypothesizes that a nutritional supplement designed for children with ASD will have a physiological action of normalizing mitochondrial function and cellular physiology throughout the body. To test whether the targeted nutritional supplement is superior to placebo, we will study 50 children, between the ages of 2 years 6 months and 17 years 3 months, with confirmed ASD and known abnormal variations in mitochondrial at baseline. Participants will be randomly assigned to receive active treatment or placebo for 12-weeks under double-blind conditions and at the end of the 12 weeks switch to the opposite treatment arm. Mitochondrial function will be measured at baseline and after each treatment arm in order to determine if the supplement positively influences cellular biochemistry.

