## 5. RESEARCH PLAN

### Trial Design

50 children with ASD and signs and symptoms of abnormal mitochondrial activity will be randomized in 1:1 ratio to receive a wide-spectrum nutritional supplement that targets mitochondrial function or placebo for 12 weeks under DBPC conditions. Each participant will serve as their own control in the cross-over design. Using a phone screen, we will identify children (age  $\geq$  2:6 and  $<$  17:3) with a diagnosis of ASD and evidence of mitochondrial function which is significantly higher or lower than average (here forth referred to as mitochondrial dysfunction). Children with suspicion of mitochondrial dysfunction will be invited to participate in a screening visit to make sure they meet including and exclusion criteria. If the screening visit is longer than 6 weeks from the prescreening, we will repeat the baseline metabolic testing to ensure an accurate baseline mitochondrial measurement. If they meet criteria, the baseline visit will be completed within 2 week but we will attempt to complete it on the same day (Table 1). Upon successful completion of the baseline visit, the participant will enter Phase 1 of the trial and will be randomized to receive active treatment or placebo for 12 weeks under DBPC conditions. At the end of the 12 weeks (end of Phase 1), the participant will return for evaluations similar to the ones conducted at baseline. Upon successful completion of the post-Phase 1 visit, the participant will start Phase 2 where they will receive active treatment or placebo, depending on what they received during Phase 1 – they will be crossed over to the opposite treatment regimen. Potential AEs, compliance and concomitant treatments will be monitored every four weeks.

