### Procedures

Randomization: Randomization will be carried out within site using permuted blocks of 4 subjects without additional stratification to nutritional supplement or placebo in a 1:1 ratio. Statisticians will prepare the permuted blocks for each site and will be sent to the Investigational Pharmacist at each site. Investigators and study staff will be blind to the allocation sequence.

**Compensation** Participants will be compensated \$50 for each of the four physical visits.

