6. **Parent Rated Autism Symptomatic Change Scale (PRASC):** The PRASC is a 12-item questionnaire that asks parent to rate changes in symptoms from “much better” to “much worse” on a 7 point Likert scale from the beginning of the intervention. This instrument was developed by [name] and Rossignol (2010) and produces a reliable measure of changes. The parent will be asked to complete this scale at each remote and onsite visit following randomization to monitor changes in ASD symptoms in the study.

Table 1. Schedule of Measures		Screening	Baseline	Double blind Phase							
Measure	Pre-Screening			*1 wk	*2 wk	*4 wk	*8 wk	12 wk	*16 wk	*20 wk	24 wk
Phase 1											
Phase 2											
Parent Ratings											
Demographics		X									
Vineland III Caregiver Form [1]			X					X			X
ABC [2]		X						X			X
PRAS-ASD [3]			X					X			X
CGSQ-Short form [4]			X					X			X
Sensory Profile 2 [5]			X								
PRASC [6]						X	X	X	X	X	X
Laboratory Assessments											
Safety Laboratory [7]	X							X			X
Biomarker Laboratories [8]	X							X			X
Pregnancy (B-HCG)	X										X
Vital Signs	X										
Height and Weight	X		X					X			X
Head Circumference	X										
Medical Assessments											
Medical/Psych History [9]		X									
Physical Exam		X									
Adverse Effects Review			X	X	X	X	X	X	X	X	X
Concomitant Treatments	X	X	X	X	X	X	X	X	X	X	X
Suicidality Assessment [10]		X	X			X	X	X	X	X	X
Compliance				X	X	X	X	X	X	X	X
Developmental Assessments											
CARS [11]		X						X			X
DAS [12]		X						X			X
OACIS [13]			X					X			X
CGI-Severity [14]			X					X			X
CGI-S-ASD			X					X			X
CGI-Improvement [15]								X			X
CGI-I ASD								X			X
Parent Target Problems [16]			X					X			X
CYBOCS-ASD [17]			X					X			X
Other Assessments											
Eye tracking task [18]			X					X			X

Full Study Title: Effect of a Wide Spectrum Nutritional Supplement on Mitochondrial Function in Children with Autism Spectrum Disorder (ASD)

Principal Investigator: [name]; Co-Investigators: [name]

Sponsor: [name]; IND 142751; ClinicalTrials.gov ID: NCT03835117; Protocol Version 02/11/2022

Funding Source: Turnabout for Autism (Private Foundation), Pleasanton CA.

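### Adverse event frequencies are to be compared by Fisher's exact test on once-per-child counts, although the cross-over gives paired data and the groups compared are not named

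*Combined protocol and SAP*

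**What the plan says.** The safety paragraph of the Statistical Analysis section gives three rules. What counts: "New events, whether presumed related to treatment or not, are classified as AEs and rated as Mild, Moderate or Severe". How often: "The occurrence of an AE will be counted once at the highest level of severity", with an example of two nausea reports from one child collapsing into the worse one. How it is tested: "The frequency of AEs by severity will be evaluated using a Fisher’s exact test". The paragraph names no groups, phase or treatment at onset, and no significance level. Its only addition is exploratory survival analysis of time to AE.

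The design is within-child. Trial Design states that "Each participant will serve as their own control in the cross-over design", and the Abstract has participants "at the end of the 12 weeks switch to the opposite treatment arm". AEs are collected in both phases: the "Adverse Effects Review" row of Table 1 has post-randomisation entries at weeks 1, 2, 4, 8 and 12 (Phase 1) and at weeks 16, 20 and 24 (Phase 2). The section on monitoring for AEs requires onset, severity and course to be logged.

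Elsewhere the protocol contrasts a supplement group with a placebo group, as in a parallel trial, but only for AEs that lead to discontinuation. No section gives a paired or per-phase AE analysis, and none limits the Fisher test to Phase 1.

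**The concern.** Fisher's exact test compares two independent groups. Here the same children supply both columns of the table, apart from any who leave before Phase 2. The counting rule adds a second problem. If a child has the same AE on supplement and on placebo and it is counted once, one treatment loses its occurrence, and no rule says which when the two grades are equal.

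At stake is the reported supplement-placebo safety comparison. Depending on how the sentence is carried out, it may have less power than the data allow, or understate AE rates with a test off its nominal level, or discard half the exposure. Because the groups are not named, the choice among these could be made after the data are seen.

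**Working it through.** **The plan's own figures.** None exists for the AE test. The only power statement (80%, effect size 0.5, alpha 0.01) concerns the primary endpoint. With 50 children, a two-sided paired t-test gives 0.799, if 0.5 is in SDs of the within-child difference; parallel groups of 25 give 0.210. The trial is therefore sized as a within-child comparison, while the AE test is not paired.

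**Inputs.** From the documents: 50 children, 1:1 allocation, two phases. Assumed, because the documents give none: AE rates, within-child correlation, a two-sided 0.05 level, and a single yes/no AE outcome.

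**Model.** Let p1 and p0 be the AE rates on supplement and placebo, and p11 the probability of the AE on both, from a bivariate normal latent variable with correlation ρ. The other cells are p1 − p11, p0 − p11 and 1 − p1 − p0 + p11. At 0.40 v 0.20, p11 = 0.080, 0.138 and 0.179 for ρ = 0, 0.5 and 0.8. The observed correlation at ρ = 0.5 is (0.138 − 0.080)/√(0.4·0.6·0.2·0.8) = 0.30.

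**(a) Pooled by phase, 50 v 50.**

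| Rates | ρ | Fisher | Exact McNemar |
|---|---|---|---|
| 40% v 20% | 0 | 0.515 | 0.498 |
| 40% v 20% | 0.5 | 0.516 | 0.658 |
| 40% v 20% | 0.8 | 0.514 | 0.829 |
| 20% v 10% | 0.5 | 0.158 | 0.244 |
| 20% v 10% | 0.8 | 0.115 | 0.315 |
| 10% v 2% | 0.5 | 0.167 | 0.205 |
| 20% v 20% (null) | 0.5 | 0.009 | 0.024 |
| 20% v 20% (null) | 0.8 | 0.001 | 0.016 |

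As an illustration, take 20 children affected on supplement and 10 on placebo. Fisher gives p = 0.049 whatever the pairing. Exact McNemar, 2·P(Bin(b + c, ½) ≤ min(b, c)), gives 2·13/4096 = 0.006 if 9 children had the AE on both (11 v 1 discordant), but 0.052 if 4 did (16 v 6).

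**(b) Counted once across both phases.** If AEs seen on both treatments are split evenly, the reported rates are p1 − p11/2 and p0 − p11/2:
- ρ = 0: 0.40 − 0.04 = 0.36 and 0.20 − 0.04 = 0.16.
- ρ = 0.5: 0.40 − 0.069 = 0.331 and 0.20 − 0.069 = 0.131.

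The 20-point difference is kept, but both rates are too low. Null rejection in simulation, crediting the first phase / crediting at random:
- ρ = 0: 4.4 / 4.4% at a 20% AE rate, 5.9 / 6.1% at 30%, 6.7 / 7.3% at 40%, 7.3 / 8.7% at 50%.
- ρ = 0.5: 4.8 / 5.5% at 30%, 5.3 / 6.7% at 40%, 5.0 / 7.5% at 50%.

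Power at 40% v 20% is 0.55, 0.58 and 0.61 for ρ = 0, 0.5 and 0.8. At 20% v 10% it is 0.23 at ρ = 0.5 and 0.24 at ρ = 0.8, against 0.24 and 0.32 for exact McNemar.

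**(c) Phase 1 only, 25 v 25.** The groups are independent and the test is valid. Power at 40% v 20% is 0.23.

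The three readings are alternatives; their losses do not add.

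**Does the replacement work?** In 1,000 simulated trials per setting, a logistic GEE with treatment and period terms and small-sample standard errors had power 0.712 and 0.883 at 40% v 20% for ρ = 0.5 and 0.8. It rejected in 2.9% at a null rate of 20% (ρ = 0.5). With an assumed 16% of children losing Phase 2, power was 0.642 (ρ = 0.5).

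Exact McNemar, which has no period term, was checked with no treatment effect and an assumed drop in recorded AEs from 30% in Phase 1 to 18% in Phase 2. It rejected in 2.2–2.8% with sequences of 25 v 25 or 26 v 24. The protocol states that "Randomization will be carried out within site using permuted blocks of 4 subjects"; with the one clinical site listed, 12 full blocks give 24 v 24 and the last two children can make it at most 26 v 24. With 24 v 14 completers, exact McNemar rejected in 2.7–3.2% and mid-p in 4.9–5.4%.

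**The case against.** The strongest reply is that the defect is conditional. The plan names no groups, and a Phase 1 comparison, for which Fisher is valid, is not ruled out; the parallel-group wording elsewhere even leans that way. This stands. A reader might infer that the plan certainly applies an invalid test, and the documents do not support that. They show an unspecified comparison, each version of which is worse than a readily available alternative.

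A second reply is that the size depends on assumptions. This also stands. At zero correlation pairing gains nothing, and for rare AEs it gains little. The Potential Risks section reports few side effects, so a common AE with a 20-point excess is a favourable case for paired analysis. The calculations use one binary outcome, whereas the plan tests frequency by severity. Under count-once, power at 20% v 10% with correlation 0.5 is nearly that of McNemar, so it would be wrong to say that count-once hides a signal; it keeps the difference and distorts the rates.

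A third concerns the five v three AE reviews. A reader might infer that this imbalance biases the comparison and makes a period term indispensable. The documents and the check do not go that far. The AE form asks about medication needs and health care encounters since the last visit, Trial Design speaks of four-weekly monitoring, and the unadjusted McNemar test held its level when sequences were balanced.

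**Conclusion.** The point holds as a should-fix matter. As written, the safety test either ignores the pairing, loses occurrences seen on both treatments, or uses half the exposure. With 50 children, a two-sided 0.05 level and assumed rates of 40% v 20%:
- pooled Fisher has power of about 0.52, against 0.50 to 0.83 for exact McNemar as latent correlation runs from 0 to 0.8;
- count-once has power 0.55 to 0.61, with both rates understated by 4 points at zero correlation and about 7 at 0.5;
- Phase 1 only has power 0.23.

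Errors on the null side differ in direction. Pooled Fisher is conservative under positive correlation (0.9% at a 20% rate and correlation 0.5). Count-once can exceed its level for AE rates of 40–50%: 6.7–8.7% at zero correlation and 5.0–7.5% at 0.5.

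A reader might also infer that participant safety oversight is compromised. It is not: the medical monitor's three-monthly review does not depend on this test. The harm is to the reported comparison.

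**What to change.** Rewrite the safety paragraph of the Statistical Analysis section:

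1. Count each AE once per child per treatment phase, at its highest severity in that phase, assigned by treatment at onset. State in advance how AEs that continue or worsen across the week-12 switch are handled. This matters because no washout is described: "Upon successful completion of the post-Phase 1 visit, the participant will start Phase 2".
2. Tabulate AEs by treatment and severity for all children exposed to each treatment.
3. Replace Fisher's test with a paired analysis of defined binary outcomes (any grade; moderate or severe). Use a logistic GEE with small-sample standard errors, or a mixed logistic model, with treatment and period terms, keeping children who have only one phase. The period term is sensible given the unequal review schedule, though not essential to hold the level when sequences are balanced.
4. Name exact or mid-p McNemar in advance as the fallback when events are too sparse for the model. At a 2% placebo rate, 0.98^50 = 36% of trials would have no placebo event.

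A carry-over sensitivity analysis is optional.

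The cost is a few sentences and one assignment rule. Onset, severity and course are already logged; one extra field may be needed if the log keeps only one severity per AE. The downsides are slightly more analysis work and a fallback that drops children with only one phase. No visit, dose or clinical procedure changes.
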